## **1.0 PURPOSE OF THE INVESTIGATION**

The aim of this multi-center study will be to assess the feasibility and safety of left atrial appendage (LAA) occlusion with the WATCHMAN FLX™ device using a standardized intra-procedural intracardiac echocardiography (ICE) protocol under moderate sedation for procedural guidance. By eliminating the need for general anesthesia, we hope to show a reduction in procedural time, decrease use of supplemental invasive procedures (central venous line, invasive arterial pressure monitoring and transesophageal echocardiography) and quicker patient recovery time. This approach can decrease healthcare resource utilization and safely simplify left atrial appendage closure with the WATCHMAN device.

## **2.0 CLINICAL PROTOCOL**

The study will be a prospective, non-randomized multicenter registry of 110 patients undergoing LAA closure with the WATCHMAN FLX utilizing an intra-procedural ICE probe under moderate sedation. The ***primary feasibility endpoint*** will be ability to successfully implant the WATCHMAN FLX device. Implant success is defined as confirmation of the device-specified release PASS (Position, Anchor, Size, Seal) criteria, successful device release, and adequate seal (defined as a residual leak <5 mm) as assessed by a core lab interpretation of the TEE (or CT) 45 days post-implant. The ***primary safety endpoint*** will be a composite of major complications (major bleeding [intracranial bleeding, or bleeding requiring blood transfusion], pericardial effusion requiring pericardiocentesis or surgery, device embolization, procedural-related stroke, or procedural related death). Additional measured end points will be: freedom from conversion to general anesthesia and/or standard TEE during implant, the incidence and the size of iatrogenic atrial septal defect on 45 day TEE (or CT). The ICE procedural images will also be collected and analyzed by an independent committee composed of non-implanting interventionalist, and an imaging specialist. The images will be graded in quality as optimal (TEE equivalent), acceptable (adequate but not as detailed as TEE), and inadequate. This prospective study, along with its endpoints will be registered in clinicaltrials.gov

## **2.1 SUBJECT SELECTION**

A total of 3 sites will enroll up to 110 consecutive patients, allowing room for 10 withdrawals to ensure data is collected on 100.

## **2.2 INCLUSION CRITERIA**

Determination for participation in the study is based on institutional standard of care practice for assessment of WATCHMAN FLX eligibility. Patients that are being considered for LAA Closure with WATCHMAN FLX device implant based on a history of non-valvular atrial fibrillation who are at increased risk for stroke and systemic embolism based on CHADS2VASc score  $>2$  but have an appropriate rationale to seek a non-pharmacologic alternative to anti-thrombotic therapy due to risks of anti-thrombotic therapy. Patients should be able to tolerate the WATCHMAN FLX device implant procedure without the need for general anesthesia.

Key inclusion criteria:

- Men and Women  $\geq 18$  years of age
- The patients is eligible to undergo WATCHMAN FLX device implant procedure
- The patient is eligible for short term anticoagulation therapy
- Ability to tolerate the procedure without the need for general anesthesia as assessed by the treating physician(s)
- Ability to give informed consent for the procedure
- The patient is able and willing to undergo the procedure under moderate sedation
- The patient is able and willing to return for required 45-day TEE or computed tomography (CT) scanning.

## **2.3 EXCLUSION CRITERIA**

No specific exclusion criteria will be implemented based on age, weight, body habitus, renal insufficiency, LAA anatomy, or the presence of sleep apnea or chronic lung disease. However, Patients will be excluded from the study if the treating physician(s) feel that general anesthesia is necessary to safely complete the procedure.

Key exclusion criteria:

- Patient has contraindication for short term anticoagulation
- The patient has history of a hypercoagulable state per medical record documentation
- Pregnancy or planning to get pregnant during the investigation

## **2.4 STUDY PROCEDURE**

**Pre-Procedure:** Informed consent should be obtained from the patient prior to the start of the procedure or within 48 hours post-WATCHMAN FLX procedure if ICE protocol is utilized. Pre-procedural planning will be according to standard WATCHMAN FLX and local institution protocols. The use of cardiac CT is encouraged and should be performed shortly before the implant procedure (within 7-10 days) based on institutional protocols. Cardiac CT should be relied on as

the initial imaging modality to determine appendage anatomy, device sizing, and to exclude the presence of a LAA thrombus. In cases where CT scan cannot be performed prior to WATCHMAN FLX procedure, LAA thrombus will be excluded intraprocedural with ICE from the right atrium and/or pulmonary artery before transseptal puncture is completed. The treating cardiologist will screen the patient and deem them suitable for attempting the procedure with moderate sedation.

**Procedure:** ICE will initially guide all implants. The ICE probe type (size, model, etc.), venous access approach (two vs. three venous accesses), access to the LA (single transseptal two probes or two different transseptal) are left to the discretion of the treating physician. However, the ICE probe will be advanced into the LA in all cases to guide the implant. It may not be possible to obtain identical views to those of TEE ( $0^\circ$ ,  $45^\circ$ ,  $90^\circ$ ,  $135^\circ$ ) with ICE. However, two orthogonal (short axis and long axis) views of the LAA should be obtained with ICE to document the position, compression, leak, and record the tug test and comply with the device release criteria (ICE-PASS). The two recommended positions to obtain short- and long- axis views are mid- left atrium and left ventricular inflow view (just underneath the mitral valve) as illustrated in Figure-1. The WATCHMAN FLX device implant will otherwise be performed in accordance with standard practice, with the Boston Scientific clinical specialist overseeing the procedure. This individual is required to document appendage anatomy characteristics, procedural times, and release criteria measurements and device compression. The WATCHMAN FLX device should not be deployed unless all release criteria are met. Indications for conversion to general anesthesia are at the discretion of the treating physicians and include, but are not limited to, hemodynamic instability, inability to maintain a protected airway during the procedure, inadequate cardiac imaging with ICE, and patient discomfort.

**Post-Procedure:** Patients should be monitored after the procedure according to institution specific protocol. Same day discharge for AM cases is allowed but not required. Patients should be maintained on a patient specific antithrombotic therapy for 45-day post-procedure based on the recommendation of the treating physician. Further anti-thrombotic changes should be made on a patient specific basis after consideration of the 45-day post-procedure TEE or CT scan and in accordance to WATCHMAN FLX device protocols.

The study specific de-identified data collection form will be used to collect procedural data and information regarding the study's primary and secondary endpoints for each case. A copy of this form, along with the pre-procedural CT imaging, procedural ICE images, and 45-day post procedure TEE or CT report should be compiled and sent to Mayo Clinic central repository database (Redcap) and Mayo Clinic Imaging Core Laboratory.

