## 2.5 Study endpoints

The **primary feasibility endpoint** will be ability to successfully implant the WATCHMAN FLX device. Implant success is defined as confirmation of the device-specified release criteria on ICE (ICE-PASS), successful device release, and adequate seal (defined as a residual leak <5 mm) assessed by TEE or CT scan at 45 days' post-implant.

The **primary safety endpoint** will be a composite endpoint of major complications (major bleeding and/or life-threatening [intracranial bleeding, or bleeding requiring blood transfusion], pericardial effusion requiring pericardiocentesis or surgery, device embolization, procedural-related stroke, or procedural related death). An event is defined as procedure related if it occurred during or within 7 days of the procedure and deemed that the event was likely related to the device/procedure. If the information is insufficient, the conservative position (assuming procedure related) should be taken.

**Secondary endpoints:** These include freedom from conversion to general anesthesia and/or standard TEE during implant, incidence, and size of iatrogenic atrial septal defect at 45 days.

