### 2.5.3 Data and Safety Monitoring Committee

There will be no data and safety monitoring committee for this registry as the WATCHMAN FLX procedure is considered standard of care with either TEE or ICE at the participating institutions. Each site is expected to monitor appropriateness and outcomes of implant.

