## 4.0 IRB INFORMATION

Each site is responsible for its own institutional review board.

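### Consent may be taken up to 48 hours after an ICE procedure, and unenrolled ICE-started cases are not accounted for, so late enrolment can depend on outcome

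*Protocol*

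**What the plan says.** Protocol section 2.4 (Pre-Procedure) states that "Informed consent should be obtained from the patient", and sets the time as "prior to the start of the procedure or within 48 hours post-WATCHMAN FLX procedure if ICE protocol is utilized". It names no other person who may consent and no other way into the registry.

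Section 2.1 sets the enrolment rule: "A total of 3 sites will enroll up to 110 consecutive patients". Sections 2.1 and 2.5.1 allow for 10 withdrawals so that data are available on 100.

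Section 2.5 defines the outcomes:
- **Primary feasibility:** three parts, namely the release criteria confirmed on ICE, release of the device, and the seal at 45 days.
- **Primary safety:** a composite that includes major bleeding, effusion needing intervention, embolization, stroke and death. An event can count as procedure related if "it occurred during or within 7 days of the procedure".
- **Secondary:** includes freedom from conversion to general anesthesia or TEE.

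Section 2.5.3 says the procedure is "considered standard of care with either TEE or ICE at the participating institutions". An ICE-guided case can therefore begin as routine care before anyone has sought study consent.

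**The concern.** Whoever seeks consent after the procedure, and the patient who gives it, may already know how the procedure went. Two of the three feasibility components and the conversion endpoint are settled when the patient leaves the room. Some safety events will also have appeared within 48 hours. If willingness to approach, or to agree, differs between good and bad outcomes, the enrolled series no longer represents the ICE-started cases.

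Some loss needs no choice by anyone. Consent is to come from the patient, so a late-route patient who dies, or is incapacitated by a stroke or intracranial bleed, has no described way in. These are components of the safety composite.

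The registry has one arm, so no comparator offsets such a bias, and the recorded rates are themselves the result. Nothing described in the protocol would let a reader check for it. Section 2.4 asks for a data form for each case but does not extend this to patients who never consented. The implant and data forms kept at sites under section 5.2 are not an enrolment log.

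**Working it through.** **The plan's own figure.** 110 enrolled − 10 withdrawals = 100 with data. This reproduces. The allowance concerns patients already enrolled and says nothing about ICE-started cases that never were. Section 2.5.1 gives no expected rate or performance goal, so there is no further calculation to reproduce.

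**What can be known when late consent is taken (sections 2.4 and 2.5)**

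| Outcome | Known by 48 hours? | Exposed to late selection? |
|---|---|---|
| Release criteria on ICE, device release | Yes | Yes |
| Conversion to general anesthesia or TEE | Yes | Yes |
| Safety events before consent | Yes, if recognised | Yes |
| Safety events after consent, to day 7 | No | No |
| Seal at day 45 | No | No |

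Patients consented before the procedure are exposed on none of these.

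**One lost patient.** Suppose 100 ICE-started cases, one of which is lost through an early procedure-related death, stroke or intracranial bleed that counts as a safety event.
- With 5 events: 5/100 = 5.0% becomes 4/99 = 4.0%.
- With 3 events: 3/100 = 3.0% becomes 2/99 = 2.0%.

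The same patient may have had the device released without conversion. If 95 of the 100 had a release, losing this one gives 94/99 = 94.9% against 95.0%, which is slightly unfavourable. The loss lowers the recorded safety-event rate but need not favour the other rates.

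**Several lost patients.** If 0/100 events were recorded (exact 95% CI 0 to 3.6%) while 3 further ICE-started cases with events went unenrolled, the full count would be 3/103 = 2.9% (0.6 to 8.3%).

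**Differential capture.** Every input here is an assumption, because the documents give none of them.
- p: true rate of a bad acute outcome (no release, conversion, or a safety event before consent). This pooled outcome is illustrative and is not a protocol endpoint.
- f: share consented late among enrolled patients without a bad acute outcome.
- r: late-route capture of patients with a bad acute outcome, relative to those without.
- Consent before the procedure is taken as independent of outcome.

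Recorded rate = p·e / (p·e + 1 − p), with e = (1 − f) + f·r.

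Examples at p = 5%, f = 0.50:
- r = 0: e = 0.50, so 0.025/0.975 = 2.6%.
- r = 1.5: e = 1.25, so 0.0625/1.0125 = 6.2%.

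Recorded rate for r = 0 / 0.5 / 1.5:

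| True rate | f = 0.10 | f = 0.25 | f = 0.50 |
|---|---|---|---|
| 3% | 2.7 / 2.9 / 3.1% | 2.3 / 2.6 / 3.4% | 1.5 / 2.3 / 3.7% |
| 5% | 4.5 / 4.8 / 5.2% | 3.8 / 4.4 / 5.6% | 2.6 / 3.8 / 6.2% |
| 10% | 9.1 / 9.5 / 10.4% | 7.7 / 8.9 / 11.1% | 5.3 / 7.7 / 12.2% |

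At r = 1, e = 1 and there is no bias. Values of r above 1 would arise if uncomplicated patients went home before being approached. Section 2.4 makes this possible ("Same day discharge for AM cases is allowed but not required"), although consent could also be sought before discharge.

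**The case against.** The strongest reply is that section 2.1 already requires consecutive patients. A site that follows it approaches everyone regardless of outcome, which removes discretionary selection and leaves a gap mainly of documentation. Part of this stands: the rule is there, and nothing shows that selection occurs. But the protocol describes no means of verifying it, and approaching everyone does not bring in a patient who can no longer consent.

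Consent arrangements may also be settled locally, since "Each site is responsible for its own institutional review board". A board might permit a representative or a waiver. So the fair statement is that no such route is described, not that these patients can never be enrolled.

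The table of recorded rates rests wholly on assumed inputs for a pooled outcome, and its range includes no bias. That objection stands: the table shows what is possible, not what is likely.

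A reader might infer three stronger points, none of which the protocol supports:
- **That early death or incapacity always flatters the results.** This holds for the safety composite when the lost patient counts as an event. It does not hold for release or conversion, where that patient may have been a success.
- **That the exclusion in section 2.3 lets converted cases be removed afterwards.** It reads "Patients will be excluded from the study if the treating physician(s) feel that general anesthesia is necessary to safely complete the procedure" and carries no time limit. But section 2.4 places the suitability screen before the procedure, and conversion is itself a secondary endpoint, so the natural reading is a judgement made beforehand.
- **That the study's conclusion could flip.** No performance goal is stated, so there is no pass or fail decision to change.

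**Conclusion.** The concern holds in a limited form. The protocol permits enrolment after acute outcomes can be known. It describes neither an accounting of ICE-started cases left out nor a route for late-route patients who die or cannot consent. The recorded release, conversion and early-complication rates can be biased as a result.

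The size and overall direction are unknown, because the documents give neither the share consented late nor the relative capture of bad outcomes. Direction is clear in one case only: loss of a late-route patient who had an early safety event lowers the recorded safety-event rate, by about one percentage point per patient at this sample size. The harm is a possibly biased estimate. It should be fixed because the rule is the protocol's own and the remedy is cheap.

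**What to change.** In section 2.4, keep the late route but add three requirements:
1. Every ICE-started WATCHMAN FLX case at the 3 sites is approached for consent regardless of outcome, including cases converted to TEE or general anesthesia.
2. The data collection form records whether consent came before or after the procedure.
3. Each site keeps a log of all ICE-started cases, with the number not enrolled and the reason (including death or inability to consent), as its IRB permits. That number is reported with the primary endpoints.

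The cost is a short log, one added field, and IRB review at each of the 3 sites, because the log covers patients who did not consent. No enrolled patient is lost and the cap of 110 is unchanged.

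The alternative is to require consent before the procedure by deleting the 48-hour clause. This is a one-line amendment that removes the late route altogether. Its cost is the loss of some patients chosen late for ICE: 0.10 × 110 = 11 if 10% would have consented late, or 0.50 × 110 = 55 if half would (both shares assumed). They would have to be replaced, so enrolment could take longer and the consecutive series could have gaps. For that reason the log comes first.

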### 2.5.2 Outcome data and data analysis

Mayo Clinic Cardiovascular Imaging Core Laboratory will do data analysis.

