## 5.0 ADDITIONAL RECORDS AND REPORTS

### **5.1 Data handling and record-keeping**

Each institution will be responsible for individual data handling and record keeping. A Data collection sheet will be used to record procedure related characteristics and track any complications. The site-specific primary investigator will be responsible for this form's accuracy and completeness. Data forms, CT, and TEE images should be de-identified and sent to the Mayo Clinic Laboratory from all participating institutions for data analysis.

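### The 45-day report and the endpoint form are routed to the core laboratory that reads the seal, with no masking specified, so the read may not be an independent check

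*Protocol*

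**What the plan says.** Section 2.4 describes a data collection form that "will be used to collect procedural data and information regarding the study's primary and secondary endpoints for each case". It then lists what travels together: "A copy of this form, along with the pre-procedural CT imaging, procedural ICE images, and 45-day post procedure TEE or CT report". These "should be compiled and sent to Mayo Clinic central repository database (Redcap) and Mayo Clinic Imaging Core Laboratory".

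Section 5.1 gives the routing a second time: "Data forms, CT, and TEE images should be de-identified and sent to the Mayo Clinic Laboratory from all participating institutions for data analysis".

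Section 2.0 defines implant success to include a residual leak below 5 mm, "as assessed by a core lab interpretation of the TEE (or CT) 45 days post-implant". Section 2.5 restates the endpoint without naming the reader; the seal is simply "assessed by TEE or CT scan at 45 days' post-implant".

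Section 2.5.2 adds: "Mayo Clinic Cardiovascular Imaging Core Laboratory will do data analysis".

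The ICE image-quality grade (three levels) belongs to a different body. Under section 2.0 the ICE images are "analyzed by an independent committee composed of non-implanting interventionalist, and an imaging specialist".

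The protocol does not say whether any reader is masked. The only protection it names for the files is de-identification.

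**The concern.** A core-lab read of the 45-day scan is valuable because it is made independently of the reading at the site. If the laboratory already holds a report on the same scan, the reader can anchor on it. Removing the patient's identity does not prevent this, because the result stays on the page.

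A leak measured against a 5 mm cut is a judgement on an image. For leaks far from the cut, a prior reading will seldom change the category. For leaks near it, a prior reading can decide the category, and the category enters the primary feasibility endpoint directly. With one group and no comparator, a shift in a favourable direction is not offset by the same shift in a control arm.

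A similar question arises for the ICE grade. Section 2.4 (Procedure) lists inadequate ICE imaging among the reasons to convert to general anesthesia, and freedom from conversion is a secondary endpoint in section 2.5, so the form should record it. A grader who saw the form could learn how the operator had judged the same images.

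**Working it through.** **The plan's own figure.** The only sample-size figure is the enrolment ceiling in section 2.5.1: 100 with data + 10 withdrawals = 110. It reproduces. The point does not rest on it, except that 100 is used as the denominator below.

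**Tracing the files for the seal read**

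| Step | Source | What is stated |
|---|---|---|
| Content of the form | 2.4 | Procedural data and primary and secondary endpoint information |
| Complications | 3.0 | Major procedural complications are reported on the form |
| Sent with the form | 2.4 | Pre-procedural CT, ICE images, 45-day TEE or CT report |
| Destination | 2.4 | REDCap and the Imaging Core Laboratory |
| Destination, second statement | 5.1 | Data forms, CT and TEE images to the laboratory |
| Seal reader | 2.0 | A core lab |
| Seal reader, second statement | 2.5 | Not named |
| Analyst | 2.5.2 | The Imaging Core Laboratory |
| Withholding or locking step | anywhere | None |

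The form and the 45-day report therefore reach the laboratory that reads the seal, and nothing written keeps them from the reader. Two assumptions enter. The core lab of section 2.0 is taken to be the Mayo laboratory, the only one the protocol names. The 45-day report is taken to state the residual leak; the protocol does not list its contents.

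**Tracing the files for the ICE grade.** Section 2.4 names two recipients, and the ICE committee is neither. Section 5.2 also has copies of images and forms go to the study's primary investigator. No section says how the images reach the committee or what comes with them. The trace stops there.

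**What can be masked.** A 45-day scan shows whether a device is in place, so release status cannot be hidden from the seal reader. The item worth withholding from that reader is the existing leak reading, with the form that may repeat it.

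**Size.** The documents give no rate of misread leaks, so only the scale can be shown. With n = 100, one changed read moves the rate by 1/100 = 1 percentage point. For illustration, take assumed success counts x with exact (Clopper-Pearson) 95% limits: lower = Beta quantile 0.025 (x, n − x + 1), upper = Beta quantile 0.975 (x + 1, n − x).

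| Assumed successes | Rate | Exact 95% CI |
|---|---|---|
| 98/100 | 98% | 93.0% to 99.8% |
| 97/100 | 97% | 91.5% to 99.4% |
| 95/100 | 95% | 88.7% to 98.4% |
| 93/100 | 93% | 86.1% to 97.1% |

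If independent reads would give 95 successes and three leaks at or above 5 mm were read as below it, the report would show 98: a shift of 3 × 1 = 3 points, with the lower limit moving from 88.7% to 93.0%. These counts are assumptions, not forecasts.

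**The case against.** The strongest reply is that the protocol is silent on masking, and silence is not evidence of an unmasked read. Sending files to an institution does not show that the reader opens them, still less before making the read. Section 5.1 sends the forms for data analysis, which need not be the reading step. A core-lab charter or an SAP, neither shown, could set the masking. This part stands. A reader might infer that the reads are not masked; the documents support only that no masking is specified and that the routing permits unmasked reads.

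A second reply is that section 2.4 could mean forms to REDCap and images to the laboratory. This fails: section 5.1 sends data forms to the laboratory explicitly. The concern therefore rests on a data flow that the protocol fixes, and not only on an unwritten policy. Any charter would have to work against sections 2.4 and 5.1 as they are worded.

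A third reply concerns the ICE grade. A reader might infer that the core laboratory grades the ICE images, or that the committee sees the form. Neither is stated. ICE grading is also absent from the endpoints listed in section 2.5, and the recordings themselves show much of the implant result. This stands, and it limits that part of the point to a gap in what is specified.

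A fourth reply is that a more basic question comes first. Section 2.4 sends a 45-day report and not the 45-day images. Section 5.1 mentions CT and TEE images without saying that they are the 45-day ones. If only a report arrives, there is no independent read to protect. That is correct, and the fix has to settle it.

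**Conclusion.** The concern holds for the seal read, in a limited form. The protocol's routing puts the 45-day report and the endpoint form in the laboratory whose read decides a component of the primary feasibility endpoint, and no safeguard is written. That weakens the read as an independent check, chiefly for leaks close to 5 mm. It does not show that any read was or will be biased.

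For the ICE quality grade, the conclusion is only that the committee's inputs are not stated, so unmasked grading is possible but not shown.

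The effect cannot be sized from the documents beyond one percentage point per changed read among 100 evaluable patients. The conclusion assumes that the laboratory of sections 2.4, 2.5.2 and 5.1 is the core lab of section 2.0, that the 45-day report gives a leak finding, and that no unseen charter overrides the routing. It is an inexpensive improvement that should be made before reads begin, because a read made with the report in hand cannot be made independent afterwards.

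**What to change.** - Amend sections 2.4 and 5.1 so that the data form and the 45-day report go to REDCap only.
- State in both sections that the 45-day TEE or CT images themselves go to the core-lab reader, under a study number. Name the core lab as the seal reader in section 2.5, to agree with section 2.0.
- Lock the seal read before it is linked to the form and report. The laboratory's analysts can then take the forms from REDCap, so section 2.5.2 can stay as it is.
- State that the ICE committee receives only the ICE images, without the form (including conversion and complication status) and without 45-day results.

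If a charter already provides this, citing it and correcting the routing in the two sections is enough. The cost is a few sentences in the protocol and a small file-routing and read-locking burden. No additional patients, scans or readers are needed.
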